1.3 Trial Design

HWFinEL is a randomised controlled trial with appropriately blinded statisticians and health economists during the conduct of the study. All analyses will be conducted by suitably qualified and experienced statisticians according to a detailed prespecified statistical analysis plan (SAP).

Participants will be randomised, after completion of their baseline questionnaire, in a 1:1 ratio to the intervention group (WBA appointment) or the control group and will be unblinded to their group allocation. Additionally, WBAs and HVs involved in service delivery, and researchers conducting the process evaluation, will be unblinded to the group allocation.

Participants who are randomised to the intervention group will be contacted by telephone (by a UCL Researcher) and invited to attend a WBA appointment within 3 months of randomisation. Wherever possible, this will be timed to coincide with their baby's/babies' 6-8 week check.

Participants who are randomised to the control group will be emailed or posted a card to their address detailing LBTH's existing 'service as usual' WBA services which reproduces what is available on their website (signposting to LBTH and voluntary sector welfare benefits advice service, national websites and helplines).

All participants will be required to complete a baseline questionnaire and a 6-month follow-up questionnaire upon study completion. Participants will be reminded twice (by email, post or telephone – telephone being the first point of contact) to complete their questionnaires: for

two months after receiving the questionnaires, if these have not been completed. Therefore, the total duration of the trial for each participant will be up to 9 months.

Additionally, a subsample of 45 participants from both groups will be purposively selected at random to complete an in-depth interview after the 6-month follow-up (refer to section 10 for more information about the interviews which forms the process evaluation).

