3.3.4 Recruitment progression criteria

Although feasibility has been demonstrated in general, and within context of this borough, in our feasibility and acceptability project, changes such as in local authority circumstances may occur and influence likely progression of the study. To address this, we will run an internal pilot. We will assess recruitment by the number of parents randomised into the trial, at the end of the first 6 months, from recruitment of the first participant, using the progression criteria outlined as a traffic light system, shown below (Table 1). Retention will be measured by completion of the 6-month follow-questionnaire, within 7 months of recruitment, allowing participants a month to complete them. Monitoring will be conducted through our governance structures.

Table 1: Progression criteria using ‘traffic light system’.

Parameter	Parameter	Traffic Light	Action
Recruitment	Recruitment of fewer than 150 parents in first six months (from first participant recruited)	Red	Trial TMG to urgently meet with TSC and inform funder. Meet with the funder to discuss the possibility of closure.
	Recruitment of at least 150 parents in the first six months (from first participant recruited)	Amber	1. Urgent TMG and TSC meeting with funder. 2. Discuss additional measures with PPI standing group. 3. Review reasons for non-referral. 4. Increase publicity including talks to local community leaders to encourage increased participation
	Recruitment of at least 230 parents in first six months (from first participant recruited). This equates to approximately one fifth of the total recruitment target.	Green	Trial to proceed
Retention	Completion of PHQ-8 follow-up questionnaire by less than half of those recruited (<50%)	Red	Trial TMG to urgently meet with TSC and inform funder. Meet with the funder to discuss the possibility of closure.
	Completion of PHQ-8 follow-up questionnaire by half (≥50%) and less than three quarters (<75%) of those recruited	Amber	1. Urgent TMG and TSC meeting with funder. 2. Review reasons for non-retention with PPI standing group. 3. Re-visit discussions with local community leaders to try to understand participation hesitation, including advertising the thank you vouchers more widely.
	Completion of PHQ-8 follow-up questionnaire by three quarters (≥75%) of those recruited	Green	Trial to proceed

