3.3.5 Recruitment period

Recruitment will begin after the assigned ethics committee has given approval to carry out the trial. A target of 1153 participants will be recruited for this trial, over a 16-month period.

This trial will be advertised at the CFCs (using a Research Ethics Committee / Health Research Authority (REC/HRA approved trial poster)) and the PPI group will support the design of recruitment materials developed alongside the Sponsor. PPI representatives will also utilise their connections within LBTH to aid recruitment.

Reporting of the trial set-up and recruitment period will be conducted on a regular basis to the HWFinEL TMG, independent trial oversight committee and the study funder. Remedial actions will be put in place if any concerns arise.

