5.2 Participant Timeline

Table 2: Schedule of Assessments

Visit Number	Screening	Baseline	Control Group	Intervention group	6-month follow up	Additional follow-up (subsample of participants)
Day/week	Day 0	2 weeks	1-3 months	1-3 months	6 months	6 months
Protocol visit window						
¹ Eligibility screen	X					
¹ Verbal Informed consent	X					
² Written informed e-consent		X				
² Eligibility confirmation	X	X				
Demographics data	X					
² Randomisation / Group allocation		X				
SAE review		X	X	X	X	
Interventions:						
³ Post card detailing LBTH services			X			

⁴ WBA appointment				X		
⁵ Questionnaires:						
EQ-5D-5L		X			X	
GAD-7		X			X	
PHQ-8		X			X	
SWEMWBS		X			X	
Subjective financial situation		X			X	
Self-reported household income		X			X	
⁶ Qualitative Interview						X

¹Initial eligibility screening will be performed by a health visitor and they will obtain verbal consent from interested participants for their contact details to be passed on to the UCL research team who can explain the study.

²Written informed e-consent, eligibility re-confirmation and randomisation will be performed by a UCL Researcher.

³Post card detailing LBTH services (information on where to access welfare benefits advice) to control group only.

⁴WBA appointment to be arranged for intervention group only (where possible to coincide with 6-8 week health check of newborn infant).

⁵Questionnaires will be completed at Baseline and 6-month follow-up. At each time point participants will be chased every 2 weeks for 2 months if the questionnaires have not been completed.

⁶A subsample of 45 participants from both groups will be purposively selected at random to complete an in-depth interview at 6 months.

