8.1 Sample Size

We make the following assumptions:

- I. We take the Minimum Clinically Important Difference (MCID) in PHQ-8¹¹ scores to be half of the usual value of 3. We have chosen this conservative estimate because the population at risk in this study is not known to have a high prevalence of depressive illness (unlike the other environments in which the PHQ-8 has been validated). Additionally, we are not convinced that this population, which encompasses a high proportion of migrants and people of minority ethnicity, will volunteer symptoms of a depressive disorder because of cultural stigma against mental illness. Further, those participants who experience symptoms of low mood may report different symptoms from those elicited on the PHQ scale due to cultural differences in the way they experience low mood. We therefore do not think the PHQ is an appropriately sensitive instrument in this environment and have estimated the sample size with a conservative estimate of the MCID.
- II. We have provided a conservative estimate of the correlation between baseline and follow-up values. This means that the study may be overpowered.
- III. We assume a standard deviation of 7.25 for the change score (which derives from the Born in Bradford study)¹⁶.
- IV. This is a very experienced research team which has conducted substantial research in this area. We have consulted extensively with our PPIE partners, and they do not think that we will encounter high dropout rates. We anticipate that we will have an approximate dropout rate of 10% but are prepared for a 20% dropout rate in our sample size calculations.
- V. We have used the ANCOVA method to calculate the sample size. This method results in a smaller sample size (if we account for baseline adjustment for PHQ-8 scores in the final analysis of the effect of the intervention) than that which would obtain otherwise.

We estimate that we will be able to detect a difference of 1.5 units in the PHQ-8 scale between the two arms with a two-sided alpha of 5% and with 90% power (assuming a nominal correlation of 0.25 between baseline and follow-up scores, a standard deviation of the change score of 7.25 and an anticipated 20% drop-out rate) with a sample size of 1153 participants.

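### The pilot retention rule uses a one-month response window where the trial collects for two, has no reading date, and turns green at a loss the sample size does not cover

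*Protocol*

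**What the plan says.** Protocol section 3.3.4 sets up an internal pilot with traffic-light criteria for recruitment and retention.

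- **Recruitment** is assessed "at the end of the first 6 months, from recruitment of the first participant".
- **Retention** is completion of the 6-month questionnaire "within 7 months of recruitment, allowing participants a month to complete them". No calendar point is named for reading it.
- **Green for retention** in Table 1 is "Completion of PHQ-8 follow-up questionnaire by three quarters (≥75%) of those recruited", with the action that the trial proceeds. Below 50% is red and leads to a discussion of closure with the funder. The band between is amber and calls an urgent meeting with the funder.

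Elsewhere the same questionnaire stays open longer. Section 1.3 runs reminders for "two months after receiving the questionnaires, if these have not been completed" and says that "the total duration of the trial for each participant will be up to 9 months". Footnote 5 to Table 2 in section 5.2 says: "At each time point participants will be chased every 2 weeks for 2 months if the questionnaires have not been completed".

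Section 3.3.5 gives the time frame: "A target of 1153 participants will be recruited for this trial, over a 16-month period". Section 8.1 anticipates about 10% dropout, "but are prepared for a 20% dropout rate in our sample size calculations". Section 5.5 restates the assumption as 10-20%.

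**The concern.** The retention criterion helps decide whether the trial continues, so it should measure what the trial needs and arrive in time to be used. Three features work against that.

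1. **Window.** A parent who answers in the second month supplies a primary outcome to the trial but is a failure under the pilot rule.
2. **Timing.** Recruitment has a reading date and retention has none. Read on the whole six-month pilot intake, the result comes late in recruitment, when the amber actions can help only part of the sample.
3. **Threshold.** Green permits a 25% loss, outside the 10-20% on which the sample size rests.

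Feature 1 makes the colour too pessimistic about final retention and feature 3 makes it too lenient, so the gate can mislead in either direction. Red also matters beyond the closure discussion: section 9.5 then redirects the economic modelling to a threshold analysis.

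**Working it through.** **Inputs.** From section 8.1: difference 1.5, SD 7.25, correlation 0.25, two-sided alpha 5%, power 90%, dropout 20%, N = 1153. From section 3.3.4: pilot intake 6 months, retention window 7 months, green at 75% or more, recruitment green at 230. From sections 1.3 and 5.2: 2 months of chasing. From section 3.3.5: 16 months of recruitment.

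**1. Reproduce the plan's sample size.**
- ANCOVA residual SD = 7.25 × √(1 − 0.25²) = 7.02.
- n per arm = 2 × [7.02 × (1.960 + 1.282) / 1.5]² = 460.2, rounded up to 461, so 922 in total.
- 922 / 0.80 = 1152.5, rounded up to 1153. This matches.
- At 10% dropout, 1153 × 0.90 = 1037.7 analysed and power is 93.1%, matching the stated 93%.

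**2. Power at the green boundary.** Power = Φ(1.5 / SE − 1.96), with SE = 2 × 7.02 / √(number analysed).

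| Retention | Analysed | SE | Power |
|---|---|---|---|
| 90% | 1037.7 | 0.436 | 93.1% |
| 80% | 922.4 | 0.462 | 90.1% |
| 75% | 864.8 | 0.477 | 88.1% |

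At 75% the trial is 922 − 865 = 57 short. Keeping 922 at 25% loss would need 922 / 0.75 = 1229.3, so 1230 randomised.

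**3. When the whole pilot cohort can be read.** Assume that the cohort is everyone recruited in the first six months.
- The last member reaches 7 months at 6 + 7 = month 13, and 13/16 = 81% of the recruitment period.
- Recruited by then at an even pace: 1153 × 13/16 = 937. With 230 at month 6 and the other 923 spread evenly over 10 months: 230 + 7 × 92.3 = 876, or 76% of 1153.
- With a two-month window, the full reading moves to 6 + 8 = month 14.

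**4. How window and threshold interact.** One-month completion = final retention × share of responders who reply in the first month.
- 75% at one month equals 80% final when the share is 0.75 / 0.80 = 94%.
- If the share were 90%, final retention of 80% would read 0.80 × 0.90 = 72%, amber for a trial on plan.
- If it were 100%, a reading of 75% would be 75% final, and green would cover a loss outside the plan.

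The protocol does not give this share, so 90%, 94% and 100% are illustrative assumptions.

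**5. What an earlier reading would rest on.** Assume even accrual within the pilot and 230 recruited.
- Two-month window, month 10: (10 − 8)/6 = 1/3, about 77 parents. Month 11: (11 − 8)/6 = 1/2, about 115.
- Existing one-month window, month 10: (10 − 7)/6 = 1/2, about 115.
- At 80% retention with 77 parents, the SE is √(0.8 × 0.2 / 77) = 4.6 points, so a 95% interval is about ±9 points.
- With green at 80% or more (62 of 77), the exact binomial chance of green is 52% if true retention is 80%, so amber is read about 48% of the time. At the anticipated 90% retention, the chance of green is 99.6%.
- With green at 75% or more (58 of 77), a trial at exactly 80% would read amber about 12% of the time.

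**The case against.** **A shorter pilot window can be a deliberate early warning.** At month 10 it makes about 115 pilot parents evaluable instead of about 77. This stands as a possible rationale, but the protocol does not give it and does not calibrate the threshold to it.

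**A progression threshold need not equal the dropout allowance.** Section 8.1 also calls its correlation conservative and says that the study may be overpowered. Both are fair. But then the protocol should say what power the green boundary accepts.

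**The power loss depends on how 7.25 is read.** The 88% treats it as the outcome SD, as the stated 1153 does. Section 8.1 words it as the SD of the change score. With correlation 0.25, the outcome SD would then be 7.25 / √(2 × 0.75) = 5.92, the residual SD 5.92 × √0.9375 = 5.73, and power at 75% retention about 97%. A reader might infer that green leaves the trial underpowered. The documents support only that it falls about two points below the protocol's own 90% on the protocol's own calculation.

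**The denominator is not absurd.** Because Table 1 divides by those recruited, a reader might infer that early readings must come out red, with recent recruits counted as failures. Section 3.3.4 defines retention per participant, within 7 months of recruitment, and nothing requires scoring a parent before that point. Nor is it an error that nobody is evaluable at month 6: only recruitment is tied to that date.

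**A late full reading follows from any six-month outcome.** This is true, and a rolling reading on the earliest recruits could start at month 7. Sections 3.3.3 and 3.3.5 also provide for tracking dropout reasons and for regular reporting with remedial action. These soften the timing point. They do not supply a date for the formal gate.

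**Conclusion.** The point holds as an alignment fault in a go/no-go rule. The contradiction between one month and two months is in the text and needs no assumption. The mismatch between 25% loss at green and 20% in section 8.1 is also textual. Its size is about 865 rather than 922 analysed and 88% rather than 90% power, given 7.25 as the outcome SD. Month 13 is derived and assumes that the retention cohort is the full six-month intake. The direction of the net error in the colour is unknown, because the first-month response share is not given. The sample size calculation, the estimand and the primary analysis are untouched. It should be corrected because the rule can trigger urgent funder meetings or a closure discussion, and because correcting it is cheap.

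**What to change.** Revise section 3.3.4 and Table 1 as one change.

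1. **Definition.** Retention = PHQ-8 completed, divided by participants whose full follow-up window has closed.
2. **Window.** Use the two-month window of sections 1.3 and 5.2. Alternatively, state that the one-month figure is an early-warning measure and calibrate its threshold to 80% final retention, giving the assumed first-month share.
3. **Reading dates.** Name an early month that still allows action, for example month 10 or 11 (about one third to one half of the pilot cohort under the two-month window). Add a confirmatory reading when the whole pilot cohort is evaluable.
4. **Threshold.** Tie green to the 80% final retention assumed in section 8.1, or keep 75% and state that it corresponds to about 88% power on the section 8.1 calculation.

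**Cost.** This is wording only, with no change to data collection. The early reading rests on few parents, about 77 of 230 at month 10. With green at 80% or more, a trial exactly at 20% loss would read amber about half the time, and amber calls an urgent meeting with the funder. The early reading should therefore be reported with its confidence interval and interpreted alongside the confirmatory one.

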3.3.5 Recruitment period

Recruitment will begin after the assigned ethics committee has given approval to carry out the trial. A target of 1153 participants will be recruited for this trial, over a 16-month period.

This trial will be advertised at the CFCs (using a Research Ethics Committee / Health Research Authority (REC/HRA approved trial poster)) and the PPI group will support the design of recruitment materials developed alongside the Sponsor. PPI representatives will also utilise their connections within LBTH to aid recruitment.

Reporting of the trial set-up and recruitment period will be conducted on a regular basis to the HWFinEL TMG, independent trial oversight committee and the study funder. Remedial actions will be put in place if any concerns arise.

3.4 Co-enrolment Guidance

Participants can be concurrently enrolled in any other interventional trial. This trial will use maintain screening and enrolment logs to track currently enrolled participants to ensure that each participant can only be enrolled once. The online randomisation service used for this trial (www.sealedenvelope.com) also prohibits the same participant from being randomised twice.

3.5 Screening Procedures and Informed Consent

3.5.1 Ways of obtaining consent to participate in HWFinEL

Informed consent will be obtained by a UCL Researcher in the following ways using a secure encrypted electronic consent (e-consent) facility, via REDCap:

- 1) By the participant completing and signing the e-consent form via a secure online link
- 2) By the participant giving verbal consent over the telephone to a member of the recruiting team, followed by completing and signing the e-consent form via a secure online link
- 3) Occasionally face to face consent may be used if assistance is required via a secure online link.

All researchers will have completed NIHR Good Clinical Practice training and those obtaining consent will additionally have completed NIHR Informed Consent Training.

Participants will be provided with a PIS and given time to read it fully. Following a discussion with a suitably trained and authorised delegate, any questions will be satisfactorily answered and if the participant is willing and has the capacity to consent and wishes to participate, informed e-consent will be obtained. Once the participant has signed the consent form, an email is generated to the delegated member of the research team, allowing them to countersign the consent form. A fully executed consent form is sent to all parties (including the participant) and is stored within REDCap (UCL Data Safe Haven). The copy within REDCap is only accessible to UCL.

Only the UCL research team can view and check the e-consent forms. UCL and CFCs will be able to view the participant's email address, telephone number and address details. This information is encrypted. Signatures are timestamped by audit trail within REDCap and cannot be altered. All actions involved in the e-consent process are recorded in the software audit trail.

If a participant has capacity and is willing to provide verbal consent, but is physically unable to sign the consent form, a witness independent of the trial team will be identified and asked to sign the witness signature field in the consent form, to attest to the participant's verbal consent to participate.

For all participants, consent will be re-sought if new information becomes available that affects the participant's consent in any way. This will be documented in a revision to the appropriate format of the Participant Information Sheet and the participant will be asked to sign an updated corresponding consent form (via a secure online link on REDCap). These will be approved by

the REC prior to their use. A copy of the approved consent form is available from the HWFinEL trial team.

Informed consent to enter and be randomised into the trial must be obtained from participants, after explanation of the aims, methods, benefits, and potential hazards of the trial and **BEFORE** any trial-specific procedures are performed.

It must be made completely and unambiguously clear that the participant is free to refuse to participate in all or any aspect of the trial, at any time and for any reason, without incurring any penalty or affecting the services available to them.

Signed consent forms must be kept by the researcher and a copy given to the participant. The consent process should be documented in the participants records.

For details on all assessments performed at each visit, please refer to Section 5.2 for Participant Timeline.

4 Trial Intervention

4.1 Introduction

The intervention is welfare advice sessions which will run alongside routine service within HV services rather than council offices or online. Co-located WBA with health appointments is an example of a Health Justice Partnership (HJP)⁸, found to be an effective tool in addressing health equity.

Successful implementation relies on collaborative working, characterised by willingness to work together, confidence in and trust between teams, and workability of systems. Establishing the intervention requires active promotion, ongoing opportunities to learn about the partnership, informal and formal interactions to build shared knowledge and understandings, and regular feedback between the teams involved⁹. To achieve this we will adapt the Glasgow model¹⁰ and set up and coordinate intervention oversight groups to provide strategic direction, operational guidance and facilitate local collaboration at the site level.

4.2 Intervention Arm

Parents randomised into the intervention arm will be offered an appointment with the borough's WBA. WBA appointments will be scheduled by the UCL researchers to coincide their baby's/babies' 6-8 week check, when possible. HVs deliver 6-8 week checks at the CFCs in Tower Hamlets. The researcher will book this appointment as they will be responsible for checking consent has been obtained, the baseline questionnaire has been completed, and then randomising the participant. They will also check which of the CFC sites are most suitable for the participant to attend for their appointment at the time of booking. There are 12 CFCs in Tower Hamlets, but we will use 8 of these. Each site will host a WBA one day a week. These centres are ideally placed to co-locate WBA as they are universally accessible to parents and children.

Advice (including welfare benefits, employment, housing, debt) will be provided by Local advice provider (WBA) under subcontract to the study (Mary Ward Legal Centre) and will proceed as per service standard. For straightforward cases this is a one off appointment; for others with multiple needs it may include subsequent appointments or referral to a more specialist advice service. The WBA will determine this on a case-by-case basis. As per service standard the advisor will work with the client until optimum financial change has been achieved. A translator will be available during advice sessions when necessary utilising the usual service in that CFC. We have recruited Mary Ward Legal Centre to add capacity in the borough. At present there are approximately 24 advice services run by voluntary and public sector organisations but none are targeted at parents of newborn children by being delivered alongside routine health appointments. Accessing WBA at present requires a high level of digital literacy and information is fragmented across various delivery organisations and websites. Two new full-time members of WBA staff will run in CFCs on days to coincide with child health checks. Approximately 20 x 1 hour appointments will be provided per working week, including some additional follow up work, suggesting that 12-15 new parents could be seen each working week. The service will run for 12-16 months or until sample size has been reached and final participant has completed their participation in the trial.

Enrolment in the trial does not preclude participants seeking financial support from other sources. We will record access to financial support on follow-up to explore uptake of financial support from any service irrespective of randomisation arm.

